3.1.2.1. Local Reactions Within 7 Days After Vaccination

The local reactions include redness, swelling, and pain at the injection site from Day 1 through Day 7 after vaccination, where Day 1 is the day of vaccination. Any reported reactogenicity events in the AE CRF during the e-diary collection period are included in the derivation discussed below.

This section describes derivations with details for the assessment of local reactions: presence, maximum severity, duration, and onset day of local reactions.

3.1.2.1.1. Presence of Local Reactions Within 7 Days After Vaccination

For the summary of the presence (yes or no) of a local reaction during the interval from Day 1 through Day 7 after vaccination, the following variables will be derived for each participant included:

- Presence (yes or no) of each local reaction on any day (Day 1 through Day 7) after vaccination.

The derivation is described in Table 2.

Table 2. Derived Variables for Each Local Reaction

Variable ^a	Yes (1)	No (0)	Missing (.)
Any day (Days 1-7) after vaccination	The participant reports the reaction as “yes” on any day (Days 1-7).	The participant reports the reaction as “no” on all 7 days or as a combination of “no” and missing on all 7 days.	The participant reports the reaction as missing on all 7 days.

a. The variable will be defined for each of the 3 local reactions.

- Presence (yes or no) of any local reaction on any day (Day 1 through Day 7) after vaccination.

For any local reaction on any day, a similar definition can be applied as given in [Table 3](#).

Table 3. Derived Variables for Any Local Reaction

Variable	Yes (1)	No (0)	Missing (.)
Any day (Days 1-7) after vaccination	The participant reports any local reaction as “yes” on any day (Days 1-7).	The participant reports all reactions as “no” on all 7 days or as a combination of “no” and missing on all 7 days for all 3 local reactions.	The participant reports all local reactions as missing on all 7 days.

3.1.2.1.2. Maximum Severity of Local Reactions Within 7 Days After Vaccination

The grading of local reactions is listed in Table 4.

Table 4. Grading Scale for Local Reactions

	Mild Grade 1	Moderate Grade 2	Severe Grade 3 ^a	Grade 4 ^b
Redness	Mild grading from the e-diary per Table 1 in the protocol or mild from the AE CRF	Moderate grading from the e-diary per Table 1 in the protocol or moderate from the AE CRF	Severe grading from the e-diary per Table 1 in the protocol or severe from the AE CRF	Necrosis or exfoliative dermatitis
Swelling	Mild grading from the e-diary per Table 1 in the protocol or mild from the AE CRF	Moderate grading from the e-diary per Table 1 in the protocol or moderate from the AE CRF	Severe grading from the e-diary per Table 1 in the protocol or severe from the AE CRF	Necrosis
Pain (at the injection site)	Does not interfere with activity (mild from the e-diary or AE CRF)	Interferes with activity (moderate from the e-diary or AE CRF)	Prevents daily activity (severe from the e-diary or AE CRF)	Emergency room visit or hospitalization for severe pain at the injection site

- a. The maximum reaction size in measuring device units is 21 (10.5 cm). Any reaction size >21 measuring device units is recorded as a number that is >20 (eg, 21) in the e-diary.
- b. Grade 4 assessments should be made by the investigator using the AE severity grading scale. The assessment will be collected on the AE CRF and thus not reported from the e-diary.

The following variables are derived for each participant included in the reactogenicity analysis:

1. Maximum severity of each local reaction item on any day (Day 1 through Day 7) after vaccination.

The maximum severity (highest grading) of each local reaction within 7 days after vaccination will be derived. The maximum severity will be derived as follows:

= Missing, if values are missing for all days (Days 1-7);

- = 0, if the participant reports all reactions as “no” or a combination of missing and “no” for all days (Days 1-7);
- = *Highest grade* (maximum severity) within 7 days after vaccination (either from the e-diary or in the AE CRF), if the answer is not “no” for at least 1 day.

2. Maximum severity of any local reaction on any day (Day 1 through Day 7) after vaccination.

The maximum severity for any local reaction after vaccination will be derived as follows:

- = Missing, if values are missing for all days (Days 1-7) across all 3 local reactions;
- = 0, if the participant reports all reactions as “no” or a combination of missing and “no” for all days (Days 1-7) for all individual local reactions;
- = *Highest grade* (maximum severity) within 7 days after vaccination, if the answer is not “no” for at least 1 day for at least 1 local reaction.

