8.3.4.2. Local Reactions

During the reactogenicity e-diary reporting period, participants will be asked to assess redness, swelling, and pain at the injection site and to record the symptoms in the reactogenicity e-diary. In Substudy A, local reactions will be assessed at the injection site on the right arm.

If a local reaction persists beyond the end of the reactogenicity e-diary period following vaccination, the participant will be requested to report that information. The investigator will enter this additional information in the CRF.

Participants will be provided with a measuring device. Redness and swelling will be measured and recorded in measuring device units (range: 1 to 21) and then categorized during analysis as absent, mild, moderate, or severe based on the grading scale in Table 1. Measuring device units can be converted to centimeters according to the following formula: 1 measuring device unit = 0.5 cm. Pain at the injection site will be assessed by the participant as absent, mild, moderate, or severe according to the grading scale in Table 1.

If a Grade 3 local reaction is reported in the reactogenicity e-diary, a telephone contact should occur to ascertain further details and determine whether a site visit is clinically indicated. Only an investigator or medically qualified person is able to classify a participant's local reaction as Grade 4. If a participant experiences a confirmed Grade 4 local reaction, the investigator must immediately notify the sponsor.

Table 1. Local Reaction Grading Scale

	Mild (Grade 1)	Moderate (Grade 2)	Severe (Grade 3)	Potentially Life-Threatening (Grade 4)
Pain at the injection site	Does not interfere with activity	Interferes with activity	Prevents daily activity	Emergency room visit or hospitalization for severe pain
Redness	>2.0 cm to 5.0 cm (5 to 10 measuring device units)	>5.0 cm to 10.0 cm (11 to 20 measuring device units)	>10 cm (\geq 21 measuring device units)	Necrosis or exfoliative dermatitis
Swelling	>2.0 cm to 5.0 cm (5 to 10 measuring device units)	>5.0 cm to 10.0 cm (11 to 20 measuring device units)	>10 cm (\geq 21 measuring device units)	Necrosis

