8.3.4.3. Systemic Events

During the reactogenicity e-diary reporting period, participants will be asked to assess vomiting, diarrhea, headache, fatigue, chills, new or worsened muscle pain, and new or worsened joint pain and to record the symptoms in the reactogenicity e-diary. The symptoms will be assessed by the participant as absent, mild, moderate, or severe according to the grading scale in [Table 2](#).

If a systemic event persists beyond the end of the reactogenicity e-diary period following vaccination, the participant will be requested to report that information. The investigator will enter this additional information in the CRF.

If a Grade 3 systemic event is reported in the reactogenicity e-diary, a telephone contact should occur to ascertain further details and determine whether a site visit is clinically indicated. Only an investigator or medically qualified person is able to classify a participant's systemic event as Grade 4. If a participant experiences a confirmed Grade 4 systemic event, the investigator must immediately notify the sponsor and, if it is determined

to be related to the administration of the study intervention, further vaccinations will be discontinued in that participant.

Table 2. Systemic Event Grading Scale

	Mild (Grade 1)	Moderate (Grade 2)	Severe (Grade 3)	Potentially Life-Threatening (Grade 4)
Vomiting	1-2 times in 24 hours	>2 times in 24 hours	Requires IV hydration	Emergency room visit or hospitalization for hypotensive shock
Diarrhea	2 to 3 loose stools in 24 hours	4 to 5 loose stools in 24 hours	6 or more loose stools in 24 hours	Emergency room visit or hospitalization for severe diarrhea
Headache	Does not interfere with activity	Some interference with activity	Prevents daily routine activity	Emergency room visit or hospitalization for severe headache
Fatigue/tiredness	Does not interfere with activity	Some interference with activity	Prevents daily routine activity	Emergency room visit or hospitalization for severe fatigue
Chills	Does not interfere with activity	Some interference with activity	Prevents daily routine activity	Emergency room visit or hospitalization for severe chills
New or worsened muscle pain	Does not interfere with activity	Some interference with activity	Prevents daily routine activity	Emergency room visit or hospitalization for severe new or worsened muscle pain

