- The investigator will attempt to establish a diagnosis of the event based on signs, symptoms, and/or other clinical information. Whenever possible, the diagnosis (not the individual signs/symptoms) will be documented as the AE or SAE.

Assessment of Intensity

The investigator will make an assessment of intensity for each AE and SAE reported during the study and assign it to 1 of the following categories:

GRADE	If required on the AE page of the CRF, the investigator will use the adjectives MILD, MODERATE, SEVERE, or LIFE-THREATENING to describe the maximum intensity of the AE. For purposes of consistency, these intensity grades are defined as follows:	
1	MILD	Does not interfere with participant's usual function.
2	MODERATE	Interferes to some extent with participant's usual function.
3	SEVERE	Interferes significantly with participant's usual function.
4	LIFE-THREATENING	Life-threatening consequences; urgent intervention indicated.

An event is defined as "serious" when it meets at least 1 of the predefined outcomes as described in the definition of an SAE, NOT when it is rated as severe.

Assessment of Causality

- The investigator is obligated to assess the relationship between study intervention and each occurrence of each AE or SAE. The investigator will use clinical judgment to determine the relationship.
- A “reasonable possibility” of a relationship conveys that there are facts, evidence, and/or arguments to suggest a causal relationship, rather than a relationship cannot be ruled out.
- Alternative causes, such as underlying disease(s), concomitant therapy, and other risk factors, as well as the temporal relationship of the event to study intervention administration, will be considered and investigated.
- The investigator will also consult the IB and/or product information, for marketed products, in their assessment.
- For each AE or SAE, the investigator **must** document in the medical notes that they have reviewed the AE or SAE and have provided an assessment of causality.
- There may be situations in which an SAE has occurred and the investigator has minimal information to include in the initial report to the sponsor. However, **it is very important that the investigator always make an assessment of causality for every event before the initial transmission of the SAE data to the sponsor.**

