10.11.10.7.4. Unscheduled Visit for a Grade 3 or Suspected Grade 4 Reaction

If a Grade 3 local reaction ([Section 8.3.4.2](#)), systemic event ([Section 8.3.4.3](#)), or fever of $\geq 39.0^{\circ}\text{C}$ ($\geq 102.1^{\circ}\text{F}$) ([Section 8.3.4.4](#)) is reported in the reactogenicity e-diary, a telephone contact should occur to ascertain further details and determine whether a site visit is clinically indicated. If a suspected Grade 4 local reaction ([Section 8.3.4.2](#)), systemic event ([Section 8.3.4.3](#)), or fever ([Section 8.3.4.4](#)) is reported in the reactogenicity e-diary, a telephone contact or site visit should occur to confirm whether the event meets Grade 4 criteria.

A site visit must be scheduled as soon as possible to assess the participant unless any of the following is true:

- The participant is unable to attend the unscheduled visit.
- The local reaction/systemic event is no longer present at the time of the telephone contact.
- The participant recorded an incorrect value in the reactogenicity e-diary (confirmation of a reactogenicity e-diary data entry error).
- The PI or authorized designee determined it was not needed.

This telephone contact will be recorded in the participant's source documentation and the CRF.

If the participant is unable to attend the unscheduled visit, or the PI or authorized designee determined it was not needed, any ongoing local reactions/systemic events must be assessed at the next study visit.

During the unscheduled visit, the reactions should be assessed by the investigator or a medically qualified member of the study staff, such as a study physician or a study nurse, as applicable to the investigator's local practice, who will:

- Measure body temperature ($^{\circ}\text{F}/^{\circ}\text{C}$).
- Measure minimum and maximum diameters of redness (if present).
- Measure minimum and maximum diameters of swelling (if present).
- Assess injection site pain (if present) in accordance with the grades provided in [Section 8.3.4.2](#).

- Assess systemic events (if present) in accordance with the grades provided in [Section 8.3.4.3](#).
- Assess other findings associated with the reaction and record this on the AE page of the CRF if appropriate.
- The investigator or an authorized designee will complete the unscheduled visit assessment page of the CRF.

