3.1.2.2. Systemic Events Within 7 Days After Vaccination

Systemic events, including fever, fatigue/tiredness, headache, chills, vomiting, diarrhea, new or worsened muscle pain, and new or worsened joint pain, are reported from Day 1 through Day 7 after vaccination, where Day 1 is the day of vaccination with any study intervention. The derivations for the systemic events as described below will be handled similarly to the way that local reactions are handled for the presence for each participant, severity level, duration, onset day, and presence of severe systemic event on each and any day.

1. Presence (yes or no) of each systemic event on any day (Day 1 through Day 7) after vaccination.
2. Presence (yes or no) of any systemic event on any day (Day 1 through Day 7) after vaccination.
3. Maximum severity of each systemic event on any day (Day 1 through Day 7) after vaccination.
4. Maximum severity of any systemic event on any day (Day 1 through Day 7) after vaccination.
5. Duration of each systemic event after vaccination.
6. Onset day of each systemic event after vaccination.

The grading scale for systemic events is provided in the protocol. However, the derivation of severity of each systemic event on each day should be based on the maximum severity reported from the e-diary or AE CRF, if data are reported from both sources; or the e-diary alone if not reported from the AE CRF.

Fever is defined as a temperature of $\geq 100.4^{\circ}\text{F}$ ($\geq 38.0^{\circ}\text{C}$). The highest temperature for each day will be recorded in the e-diary. Any measure with degrees Fahrenheit will be converted to degrees Celsius for analysis. For reporting purposes, fever will be analyzed using the following temperature ranges:

- Mild (≥ 38.0 to 38.4°C from the e-diary or mild grade from the AE CRF);
- Moderate (>38.4 to 38.9°C from the e-diary or moderate grade from the AE CRF);
- Severe (>38.9 to 40.0°C from the e-diary or severe grade from the AE CRF);
- Grade 4 ($>40.0^{\circ}\text{C}$ from the e-diary or severe grade from the AE CRF, and documented $>40.0^{\circ}\text{C}$ via CRF query or other sources).

Any temperature that is confirmed as incorrect will use the correct temperature for analysis and those for which the correct temperature is unknown will not be included in the analysis.

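### SAP Table 4 footnote b takes Grade 4 local reactions from the AE severity scale, contradicting the Grade 4 column it annotates and Protocol Table 1, so a Grade 4 reaction can be analysed as Grade 3

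*SAP*

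**What the plan says.** **Protocol scale for local reactions.** Table 1 in Protocol 8.3.4.2 defines Grade 4 injection-site pain as "Emergency room visit or hospitalization for severe pain". Grade 4 redness is necrosis or exfoliative dermatitis, and Grade 4 swelling is necrosis. Participants rate pain no higher than severe. Only an investigator or medically qualified person may assign Grade 4, and a confirmed Grade 4 reaction must be notified to the sponsor at once.

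**SAP scale for local reactions.** The Grade 4 column of SAP Table 4 gives the same criteria, for pain "Emergency room visit or hospitalization for severe pain at the injection site". Footnote b to that column then says "Grade 4 assessments should be made by the investigator using the AE severity grading scale" and adds "The assessment will be collected on the AE CRF and thus not reported from the e-diary". The Grade 3 cells accept a rating of severe from either the e-diary or the AE CRF.

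**AE scale.** Protocol 10.3.3 defines Grade 4 intensity as "Life-threatening consequences; urgent intervention indicated". Grade 3 is significant interference with usual function.

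**Systemic events.** SAP 3.1.2.2 refers to the protocol for the scale. Protocol Table 2 has, for example, "Emergency room visit or hospitalization for severe headache" as Grade 4. The SAP then says that daily severity "should be based on the maximum severity reported from the e-diary or AE CRF".

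**Where the investigator's assessment is recorded.** Protocol 10.11.10.7.4 has the investigator or a medically qualified staff member assess pain and systemic events against the protocol grades at an unscheduled visit. It continues: "The investigator or an authorized designee will complete the unscheduled visit assessment page of the CRF". The telephone contact is also recorded in the CRF. Protocol 8.3.4 says e-diary data need not be entered as AEs.

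**The concern.** Table 4 gives two tests for the same grade, and they can disagree. The column asks whether a defined event occurred, such as an emergency room visit. The footnote asks how the investigator rated the event on a general intensity scale whose top category is life-threatening. A programmer who follows the footnote and one who follows the column can grade the same participant differently, and the SAP does not say which governs.

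Maximum severity is how the primary reactogenicity endpoint is presented (Protocol 10.11.11.3.2; SAP 6.1.3.1). If the footnote is applied, the Grade 4 row can omit a reaction that the investigator confirmed as Grade 4 under Table 1 and notified to the sponsor as such. The table and the sponsor's own safety notifications would then differ, with nothing in the SAP to explain why.

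**Working it through.** The documents give no expected Grade 4 count, so there is no planned figure to reproduce. The check is a comparison of texts, followed by a simple calculation of what one event does to the row.

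**1. The definitions for injection-site pain, side by side**

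| Place | Grade 3 | Grade 4 |
|---|---|---|
| Protocol Table 1 | daily activity prevented | "Emergency room visit or hospitalization for severe pain" |
| SAP Table 4, cells | daily activity prevented; severe in e-diary or AE CRF | "Emergency room visit or hospitalization for severe pain at the injection site" |
| Protocol 10.3.3, AE intensity | significant interference with usual function | "Life-threatening consequences; urgent intervention indicated" |

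Footnote b does not cite Protocol 10.3.3. That section holds the protocol's general AE intensity scale, completed on the AE page, so I take it to be the scale meant.

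**2. A case that separates them.** A participant goes to the emergency room for severe injection-site pain on Day 2 and is discharged.

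- Protocol Table 1: Grade 4.
- SAP Table 4, column: Grade 4.
- SAP Table 4, footnote b: the investigator applies the AE scale. The event is not life-threatening, so severe is a proper entry, and Table 4 maps an AE CRF entry of severe to Grade 3.

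**3. Does the highest-grade rule help?** SAP 3.1.2 accepts that the e-diary and AE CRF may grade differently and takes the higher. The e-diary stops at severe (3). If the AE CRF also says severe (3), the maximum is max(3, 3) = 3. The rule cannot produce a grade that neither source contains.

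**4. Does hospitalization help?** Admission makes the event an SAE, so an AE record exists. But Protocol 10.3.3 separates seriousness from intensity, so the record may still carry severe. The larger capture gap is the emergency room visit without admission.

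**5. Systemic events.** Footnote b belongs to the local-reaction table and does not apply. Of the eight systemic events, fever has its own route: the SAP assigns Grade 4 from an e-diary temperature above 40.0°C, or from an AE CRF grade of severe with such a temperature documented. Vomiting needs hypotensive shock for Grade 4, so it does not fit the simple example. For the other six (diarrhea, headache, fatigue, chills, muscle pain, joint pain), Table 2 uses an emergency room visit or hospitalization for the severe symptom. The SAP takes severity from the e-diary and AE CRF and does not say how an AE rated severe becomes Grade 4.

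**6. What one event does.** Inputs: 150 per group (Protocol Table 4) and Clopper-Pearson 95% limits (SAP 6.1.3.1), assuming all 150 transmit some e-diary data.

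- 0/150 = 0%. Upper limit = 1 − 0.025^(1/150) = 2.4%.
- 1/150 = 0.67%. The upper limit solves (1 − p)^150 + 150p(1 − p)^149 = 0.025, giving p = 3.7%.

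These limits show how sensitive the row is to one event. They do not estimate how often misgrading would occur.

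**The case against.** The strongest reply is that the SAP already carries the right definition. The Grade 4 column repeats Protocol Table 1, and if the column governs, the emergency room visit is Grade 4. This stands, and it limits the finding. A reader might infer that the SAP replaces the protocol's definition and that such reactions are always counted as Grade 3. The documents support only that they can be, because the column and its footnote conflict and no rule ranks them.

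A second reply is that the scales are closer than they look. Protocol Tables 1 and 2 head the Grade 4 column as potentially life-threatening, so an investigator who has confirmed Grade 4 might choose the top AE category. That is plausible, but the wording of the AE scale does not require it, and the analysis grade should not depend on that choice.

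A third is that footnote b expressly sends Grade 4 to the AE CRF, so the statement that e-diary data need no AE entry is not decisive. This is fair: a Grade 4 assessment is not diary data. What remains is that the entry is made on the AE scale, while the assessment against the protocol grades at an unscheduled visit goes on a CRF page that the severity derivations do not name.

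A fourth is that the CRF itself is not among the documents. We cannot confirm that the unscheduled-visit page has a Grade 4 field, and a telephone contact may confirm Grade 4 instead of a visit. This also stands, and the fix is worded to allow for it.

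A reader might also apply footnote b to headache or fatigue, or pool Groups 1 and 2 to 300 when judging size. Neither is supported: the footnote covers local reactions only, and reactogenicity is reported for each of the seven groups separately.

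**Conclusion.** The concern holds in a limited form. SAP Table 4 contradicts itself on Grade 4 local reactions, and its footnote also contradicts Protocol Table 1. Followed literally, the footnote allows a non-life-threatening reaction that meets the Table 1 criterion to be analysed as Grade 3, most clearly an emergency room visit without admission for injection-site pain. For six systemic events the problem is an omission: the protocol scale is cited, but no step from the AE CRF to Grade 4 is given.

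The expected number of affected events is small. Each would still be counted as severe and in the any-severity row, and the stopping rules in Protocol 10.11.10.5 do not use reactogenicity Grade 4. The effect is on one row of a primary safety table, where a single event per group takes the estimate from 0% to 0.67%.

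The conclusion assumes that footnote b means the Protocol 10.3.3 scale and that an investigator may rate such an event severe. It should be corrected before the analysis, but it does not threaten the trial's main conclusions.

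**What to change.** 1. Reword SAP Table 4 footnote b so that analysis Grade 4 is assigned when the investigator confirms that the Protocol Table 1 criterion is met. Do not make the AE scale's life-threatening category the test.
2. State in SAP 3.1.2.2 that the Protocol Table 2 criteria govern Grade 4 for systemic events other than fever. Leave the fever rule as it is.
3. In SAP 3.1.2, 3.1.2.1.2 and 3.1.2.2, name the existing CRF records of investigator confirmation as sources for maximum severity: the AE CRF, the unscheduled-visit assessment page and the telephone-contact record, as far as each captures the grade. Check the CRF first to see which of them do.

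The cost is SAP wording and one more input to the reactogenicity derivation. No new data are collected and no clinical procedure changes. The Grade 4 count may become slightly less favourable.
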